## **Objectives**

Tailoring evidence-based interventions for delivery in community-based mental health services for youth with autism spectrum disorder (ASD) has the potential to increase quality of care and improve child outcomes. Results from the current study will serve as the foundation for large-scale hybrid implementation and effectiveness trials and a generalizable approach for different service systems of care and clinical populations. Youth with ASD represent a growing population with significant service needs. Prominent among these needs are high rates of co-occurring psychiatric conditions that contribute to increased functional impairments and often necessitate mental health services. Executive functioning deficits are associated with ASD as well as common co-occurring conditions (e.g., attention-deficit/hyperactivity disorder) and an evidence-based intervention has been developed and tested to address executive functioning within the school context. There is an urgent need to implement indicated evidence-based interventions for youth with ASD receiving care in community mental health settings. Interventions that optimally “fit” the mental health services context as well as the complex and co-occurring mental health needs of these youth have the potential to improve key clinical outcomes for this high priority population.

## **Objectives**

Specific objectives are to (1) conduct a need and context assessment to inform the systematic adaptation an executive functioning evidence-based intervention; (2) systematically adapt the clinical intervention and develop a corresponding implementation plan, together entitled “Executive Functioning for Enhancing Community-based Treatment for ASD,” (EFFECT for ASD); and (3) conduct a feasibility pilot test of EFFECT for ASD in community mental health settings.

## **Methods**

This mixed-methods developmental study will apply the Exploration, Preparation, Implementation, Sustainment implementation framework and a community-academic

partnership approach to systematically adapt and test an evidence-based executive functioning intervention for youth with ASD for delivery in community mental health settings. See Dickson et al., 2020 in the 'References module' for a detailed description of all methods throughout the multi-aim study.

### **Statistical Plan**

Descriptive analyses and examination of qualitative themes related to perceptions of the feasibility, acceptability, and appropriateness of *Unstuck and On Target* will be used to evaluate intervention effectiveness and implementation outcomes. For quantitative implementation outcome measures, criteria for determining sufficient feasibility, acceptability, and appropriateness will be applied, including examination of mean-level ratings on relevant measures and whether mean scores are greater than or equal to ratings indicating perceived feasibility, acceptability and/or appropriateness (e.g.,  $\geq 4$  on Feasibility and Acceptability of Interventions measures,  $\geq 4$  on subscales on the Perceived Characteristics of Intervention Scale). Scores will also be compared to prior relevant literature. For example, fidelity scores will also be analyzed and compared to prior trials of *UOT* to determine if providers achieve similar fidelity levels, indicating appropriate uptake and fidelity. Finally and informed by current recommendations and prior work, objective measures of outcomes (e.g., recruitment and enrollment, proportion of sessions completed, attrition) will also be examined. Intervention effects analyses will also be conducted, including Group (intervention vs. control) x Time (pre to post), will be conducted to examine changes in outcome measures over time; analyses will be conducted using recommended procedures (e.g., maximum likelihood) to adjust for missing data and non-normality of outcome variables. Informed by similar pilot feasibility trials, the targeted sample size (n=26) allows for dropout rates similar to that of prior pilot studies in the same setting while also meeting the threshold for sufficiently precise parameter estimates. Per current recommendations, direction of effects and effect size estimation will be examined given the small sample size. Consistent with a Type III Scale-Out, this pilot study adapts an evidence-

based intervention for a new population and delivery systems and will borrow statistical strength by comparing findings to prior studies regarding evidence of *UOT*. As such, we anticipate an effect size that approximates the medium effect observed in the *UOT* randomized-clinical trial (average Cohen's  $d = .55$ ).

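### Does comparing the observed mean rating with a benchmark of 4, with no interval, rater count or missing-rating check, undermine the feasibility conclusion?

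*Combined protocol and SAP*

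**What the plan says.** The Statistical Plan opens with a descriptive and qualitative evaluation: "Descriptive analyses and examination of qualitative themes related to perceptions of the feasibility, acceptability, and appropriateness". For the quantitative implementation measures it says that "criteria for determining sufficient feasibility, acceptability, and appropriateness will be applied, including examination of mean-level ratings on relevant measures", and then asks whether "mean scores are greater than or equal to ratings indicating perceived feasibility, acceptability and/or appropriateness". The cut-off of 4 or more is an example, given for scores "on Feasibility and Acceptability of Interventions measures" and for subscales of a perceived-characteristics scale.

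The same section sets other evidence beside the mean. "Scores will also be compared to prior relevant literature", fidelity is compared with earlier trials of the intervention, and "objective measures of outcomes (e.g., recruitment and enrollment, proportion of sessions completed, attrition) will also be examined".

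Two further statements bear on precision and missing data. The target of 26 is said to allow for dropout "while also meeting the threshold for sufficiently precise parameter estimates", but no parameter or width is named. On missing data, "analyses will be conducted using recommended procedures (e.g., maximum likelihood) to adjust for missing data and non-normality of outcome variables"; this belongs to the sentence on Group x Time intervention effects. The Methods section refers the reader to an external publication for the detailed methods.

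**The concern.** The mean rating is the only criterion in the section with a numerical cut-off, and it is applied to the observed mean alone. The section states no SD or interval, no number of raters out of those expected to rate, and no step for missing ratings. The maximum-likelihood statement covers a different analysis. Attrition counts participants lost, which need not equal ratings not returned.

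Read literally, a mean of 4.1 would get the same verdict from a few completers as from everyone expected to rate. That could matter because the third objective is a feasibility pilot, and the Objectives section says the results will underpin larger hybrid trials. Someone planning the next trial might not be able to tell a secure result from one that the data cannot separate from a mean below 4. If people who left early would have rated lower, the observed mean would also lean towards success.

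**Working it through.** **No stated figure to reproduce.** The plan gives no precision or error rate for the rating criterion. The documents do not say who rates, how many rate, what the 26 units are, how ratings vary or how many will be missing. The figures below therefore rest on assumptions: independent raters, roughly normal ratings, SD of 0.5, 0.7 or 1.0, and 26 raters (the target sample size) or 13 (half of it).

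**Step 1: precision of a mean rating.** The 95% half-width is t(n−1, 0.975) × SD/√n. The chance that a true mean of 3.8 reaches the cut-off is 1 − Φ(0.2√n/SD). Under normality, a true mean of 4.2 misses it equally often.

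| Raters | Half-width, SD 0.5 / 0.7 / 1.0 | P(observed mean ≥ 4), true mean 3.8 |
|---|---|---|
| 26 | 0.20 / 0.28 / 0.40 | 0.02 / 0.07 / 0.15 |
| 13 | 0.30 / 0.42 / 0.60 | 0.07 / 0.15 / 0.24 |

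Sampling error alone therefore does not favour success.

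**Step 2: missing ratings.** Let m be the observed mean and p the share missing. The overall mean falls below 4 when non-raters average less than r = (4 − (1 − p)m)/p. The shortfall against raters is then m − r = (m − 4)/p.

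For m = 4.1:
- p = 0.1: r = (4 − 3.69)/0.1 = 3.10, a shortfall of 1.0
- p = 0.2: r = (4 − 3.28)/0.2 = 3.60, a shortfall of 0.5
- p = 0.3: r = (4 − 2.87)/0.3 = 3.77, a shortfall of 0.33

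For m = 4.3 the shortfalls are 3.0, 1.5 and 1.0. For m = 4.5 they are 5.0, 2.5 and 1.67. Missing ratings could reverse the reading mainly when the mean is just above 4 and about 20% or more are missing.

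**Step 3: would a stricter rule help?** One option is to mark a mean of 4 or more as imprecise when its 95% interval includes values below 4. That happens exactly when a two-sided 5% test fails to reject a mean of 4, so the label is a test under another name. The share of results marked is P(mean ≥ 4) − P(T > t(n−1, 0.975)), where T is noncentral t with noncentrality (μ − 4)√n/SD.

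With 26 raters and a true mean of 4.2:
- noncentrality: 0.2 × √26/SD = 2.04 / 1.46 / 1.02
- share of all results marked: 0.479 / 0.639 / 0.682
- share meeting the benchmark: 0.979 / 0.927 / 0.846
- share marked among those meeting it: 0.479/0.979 = 49%, 0.639/0.927 = 69%, 0.682/0.846 = 81%

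The label would fall on about half to four fifths of the results that meet the benchmark when the true mean is above it. It would mostly repeat that the sample is small, which the plan already acknowledges.

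**Step 4: does anything turn on the cut-off?** The mean rating is introduced with a word that makes it one item in a set. No rule says the programme proceeds if the mean reaches 4 and stops if it does not. Reporting an interval and a count leaves each comparison with 4 as it was.

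**The case for a change.** The strongest case for a change is that it is cheap. An interval, a denominator and a one-line break-even value for non-raters need a few lines of text and no new data. Descriptive work still needs precision and a denominator, and neither qualitative themes nor attrition shows how precise a mean is or whose ratings are absent. The maximum-likelihood sentence and the precision remark do not fill the gap.

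Most of this stands as reporting advice. The text does leave these items unstated, and a good report would include them. If raters are clustered, for example within clinics, a simple interval would be too narrow, so an analyst would have to allow for that.

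What does not stand is the step from silence to defect. The plan promises descriptive analyses and rules out no summary of spread or count. Attrition is to be examined alongside the ratings, so a completers-only mean would not be read in ignorance of dropout. The external methods paper may hold more detail, but it cannot be seen here and nothing rests on it.

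**Conclusion.** No change to the plan is needed. The observation is accurate, but it describes reporting detail left unstated in a small descriptive pilot, not a wrong rule. Analysts would ordinarily give each mean with its SD, an interval and the number of raters out of those expected, and the plan leaves them free to do so. Doing so would change no comparison with the benchmark. A formal imprecision label would add a significance test to a criterion meant to be read descriptively, at the cost shown in step 3.

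The possible effect is confined to means near 4. On the assumptions above, a true mean of 3.8 reaches the cut-off 2% to 15% of the time with 26 raters and 7% to 24% with 13. An observed 4.5 is reversed by 20% missing ratings only if non-raters average 2.5 points lower. SD, rater number, independence, normality and missingness are all assumed, so the actual size cannot be judged from the documents. Nothing in them indicates that ratings will fall near 4 or that many will be missing.

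### If allocation is random, a baseline-adjusted effect estimate would be modestly more precise than the plain Group x Time contrast, at almost no cost

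*Combined protocol and SAP*

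**What the plan says.** The Statistical Plan describes the between-group comparison in one sentence: "Group (intervention vs. control) x Time (pre to post), will be conducted to examine changes in outcome measures over time". It adds that "analyses will be conducted using recommended procedures (e.g., maximum likelihood) to adjust for missing data and non-normality of outcome variables". No baseline covariate, ANCOVA or shared baseline mean is named. The likelihood method is offered for missing data and non-normality, not for baseline adjustment.

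On size, the plan says that "the targeted sample size (n=26) allows for dropout rates similar to that of prior pilot studies in the same setting". It gives precision as a second ground for this number, which it describes as "meeting the threshold for sufficiently precise parameter estimates". On purpose, it states that "direction of effects and effect size estimation will be examined given the small sample size". The result is to be set against a Cohen's d of .55 from the earlier randomized trial of the same intervention.

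The document does not say how participants come to be in the intervention or control group. The Methods section sends the reader to an external publication for full methods, which is not available here.

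**The concern.** A Group x Time term with two time points and complete data equals the difference between groups in mean change. That fixes the slope of post on baseline at 1. When the true slope is below 1, the estimate over-corrects for baseline and stays correlated with whatever baseline difference arose by chance. ANCOVA estimates the slope from the data and removes that dependence.

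Maximum likelihood does not resolve this by itself. In the ordinary Group x Time model each group has its own baseline mean, so the imbalance stays in the estimate when some post scores are missing too.

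The stake is small. This is a feasibility pilot, effect estimates are secondary, and no feasibility, acceptability or appropriateness criterion depends on the choice. But the plan defends its sample size by precision and intends to read the direction and size of effects from about 26 participants. Choosing the estimator is one of the few ways to gain precision without recruiting anyone.

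**Working it through.** **The plan's own figure.** n=26 cannot be reproduced: no SD, dropout rate, interval width, alpha or power is given. For orientation, detecting d = 0.55 with 80% power at two-sided 5% needs 52 per arm, and 13 per arm gives power of 0.29. So 26 is not a power-based number, and the plan does not claim that it is.

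**Inputs.** From the document: n=26, two time points, maximum likelihood, d = .55. Assumed: random 1:1 allocation, n=26 means youth in total, no clustering, SD = 1 at both times unless stated, and pre-post correlation rho from 0.3 to 0.9. In the dropout case, 10 of 13 per arm have post scores (3/13 = 23% lost, completely at random).

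**Formulas.** Let n0 be baselines per arm, n1 post scores per arm, and N = 2 x n1.

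- Adjusted (ANCOVA): Var = (1 - rho^2) x (2/n1) x (N-3)/(N-4). The last factor is the cost of estimating the slope.
- Group x Time by unconstrained maximum likelihood: the estimate is the completers' ANCOVA estimate plus (b - 1) x D, where b is the pooled slope and D the baseline difference among all participants. Var = (1 - rho^2) x [2/n1 + 2 x (1/n1 - 1/n0)/(N-4)] + (1 - rho)^2 x 2/n0. With complete data this reduces to 2(1 - rho) x 2/n, the variance of a difference in mean change.
- Half-width = SE x t(0.975), with N-3 df for adjusted and N-2 df for Group x Time (approximate under dropout).

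**Worked case, rho 0.5, complete data (13 per arm).** Group x Time: 2 x 0.5 x 2/13 = 0.154, SE 0.392, half-width 0.81. Adjusted: 0.75 x 2/13 x 23/22 = 0.121, SE 0.347, half-width 0.72. Variance ratio 0.78. Equivalent sample size: 26/0.784 = 33.

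**Worked case, rho 0.5, 10 post scores per arm.** Group x Time: 0.75 x [0.2 + 2 x (0.1 - 0.0769)/16] + 0.25 x 2/13 = 0.191, SE 0.437. Adjusted: 0.75 x 0.2 x 17/16 = 0.159, SE 0.399. Variance ratio 0.84.

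| rho | Variance ratio, complete | Half-width (SD), complete | Variance ratio, dropout | Half-width (SD), dropout |
|---|---|---|---|---|
| 0.3 | 0.68 | 0.96 to 0.79 | 0.74 | 1.07 to 0.93 |
| 0.5 | 0.78 | 0.81 to 0.72 | 0.84 | 0.92 to 0.84 |
| 0.7 | 0.89 | 0.63 to 0.59 | 0.92 | 0.72 to 0.69 |
| 0.8 | 0.94 | 0.51 to 0.50 | 0.97 | 0.59 to 0.58 |
| 0.9 | 0.99 | 0.36 to 0.36 | 1.01 | 0.42 to 0.42 |

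Ratios are adjusted over Group x Time; half-widths run from Group x Time to adjusted. At rho 0.7 with complete data the equivalent sample is about 29.

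**Where the gain ends.** Complete data: (1 + rho)/2 x 23/22 = 1 gives rho = 0.913. With dropout the break-even is 0.882.

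**Sensitivity.**

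- If 26 is per arm (complete data), the ratios are 0.66/0.77/0.87/0.92/0.97.
- With unequal SDs (k = post/pre, 13 per arm), the ratio is k^2 x (1 - rho^2) x (23/22)/(1 + k^2 - 2 x rho x k). For k = 0.8: 0.52/0.60/0.66/0.67/0.64. For k = 1.25: 0.82/0.93/1.03/1.05/0.99, so there is no gain for rho of about 0.64 to 0.90, and the loss is at most about 5%.

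**Simulation check.** With 200,000 trials per setting and a true effect of 0.55, the ratios were 0.680/0.784/0.888/0.940/0.992 (complete) and 0.744/0.836/0.926/0.968/1.007 (dropout). All means lay between 0.549 and 0.551, and ANCOVA interval coverage was 0.949 to 0.951. With dropout at rho 0.5, the correlation of the estimate with the baseline difference was -0.45 for Group x Time and 0.00 for ANCOVA. In five directly fitted data sets, the common-baseline likelihood estimate agreed with the completers' ANCOVA to four decimals.

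**The case against.** The strongest reply is that the plan does not spell out its model. It introduces Group x Time with the word *including*, never says the baseline means are unconstrained, and refers to an external publication for detail. A common-baseline model is itself a form of Group x Time likelihood model, so the wording could accommodate the fix. That is fair, and it is why the point is an improvement and not a fault. But an ordinary Group x Time model has separate baseline means, and nothing in the document indicates otherwise.

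Second, nothing says that this pilot is randomized. Without random allocation, a common baseline mean is not justified, and the adjusted and change analyses can estimate different things. This stands, and the recommendation is conditional for that reason.

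Third, almost every input is assumed, clustering by provider is not modelled, and the reading hardly moves: for an observed effect of 0.55 SD, in all ten tabulated cases zero lies inside both intervals or outside both. The precision statement is also not tied to this contrast in particular. These points stand and limit the importance; they do not reverse the direction of the gain in the main case.

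Finally, the document does not say how the earlier d of .55 was computed, so a change of estimator could help or harm that comparison. Reporting both estimates covers this.

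**Conclusion.** The point holds as a low-priority improvement. Under random 1:1 allocation of 26 independent youth with equal SDs, baseline adjustment lowers the variance by about 32% to 6% for rho from 0.3 to 0.8 with complete data, and by about 26% to 3% with 10 post scores per arm. It gives essentially nothing at rho 0.9 and can lose up to about 5% of variance if the post SD is 1.25 times the pre SD. The interval stays wide against 0.55 either way. Group x Time is not biased under randomization. Confidence is medium, because allocation, rho, the SDs and the unit of n=26 are not given, and the external publication may settle some of them.

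**What to change.** State in the SAP how participants are assigned to intervention or control, and bring in any model details that are given only in the external publication.

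- **If allocation is random:** make the main effect estimate the post score adjusted for its own baseline. Alternatively, use the maximum likelihood model with a common baseline mean; with complete baselines and an unstructured covariance this gives the same estimate. Report the effect size with a 95% CI and keep unconstrained Group x Time as a sensitivity analysis.
- **If allocation is not random:** keep Group x Time as the main estimate and show the adjusted one beside it.

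The cost is one or two sentences on the estimator, about one degree of freedom and no new data, with the possible small loss of precision described above.
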